6.1.5 Sensitivity Analyses of Primary Efficacy Endpoint

Sensitivity analyses will be performed to evaluate the robustness of the primary analysis results as further described in this section.

6.1.5.1. Missing Data Analyses Based on Multiple Imputation

- The missing data of the GA area are filled in 100 times to generate 100 complete datasets by the pattern mixture model method and the tipping point analysis method, respectively, as described in [Section 4.6.5](#).

- The 100 complete datasets, imputed by either the pattern mixture model method or the tipping point analysis method, are analyzed by using the same approach as for the primary analysis for the primary efficacy endpoint in [Section 6.1.3](#).
- The results from the 100 complete datasets are combined to generate the estimates as described in [Section 6.1.3](#).

6.1.5.2. Per Protocol Set

The main analysis described in [Section 6.1.3](#) will be repeated using the PP Set to investigate the impact of changing the population on the estimand.

The summary and presentation of the observed values for the total area of GA lesion(s) by treatment group and visit described in [Section 6.1.3](#) will be repeated using the PP Set.

6.1.5.3. Other Sensitivity Analyses

The main analysis described in [Section 6.1.3](#) will be repeated with the following modifications:

- **Square root of the GA lesion area:** using the change from baseline in the square root of the GA lesion area instead of the change from baseline in the GA lesion area as response variable and replacing baseline GA lesion area by square root of baseline GA lesion area in the model.
- **Restriction on baseline area:** subject eyes are included only if GA lesion at baseline exceeds 0.5 mm².
- **Only first 12 months:** excluding all data points after the 12-month visit.
- **Absolute change at Month 24:** using change from baseline in GA lesion area as response variable, assuming time as categorical, for both the GA area and the square root of GA area. Replacing baseline GA lesion area by square root of baseline GA lesion area in the model for analysis of the square root of GA area.

The LS mean of the change from baseline in GA area (mm²) of Eligible Eyes \pm the standard error will be plotted over time by treatment group, assuming time as categorical.

- **Percentage change at Month 24:** using percentage change from baseline in GA lesion area as response variable, assuming time as categorical, for both the GA area and the square root of GA area. Replacing baseline GA lesion area by square root of baseline GA lesion area in the model for analysis of the square root of GA area.
- **Exclusion of eyes with CNV at baseline or historical determined by PI:** Eligible Eye(s) reported to have CNV at baseline or in medical history will be excluded from the analysis.

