4.0. STATISTICAL ANALYSIS CONVENTIONS AND DEFINITIONS

4.1. Reporting Conventions

Individual subject data obtained from electronic case report forms (eCRFs), external sources, and any derived data will be presented in data listings by subject.

Continuous measures will be summarized by number of observations, minimum, first quartile (Q1), median, mean, third quartile (Q3), maximum, and standard deviation (SD). The minimum and maximum will be presented at the same level of precision (decimal point) of the measurements. Median, Q1 and Q3, and mean will be presented at one greater level of precision (decimal point) as the measurements. SD will be presented at two greater levels of precision. In general, the number of decimal places should not exceed 3 decimal places unless appropriate. Confidence intervals (CIs) will be provided with the same decimal places as the point estimate, unless otherwise specified, in the tables and listings.

Categorical (including binary) measures will be summarized by count and percent. Categories for which counts are 0 will be displayed for the sake of completeness. For example, if none of the subjects discontinue due to “lost to follow-up”, this reason will be included in the table with a count of 0. A row denoted as “Missing” will be included in the count tabulations where necessary to account for dropouts or missing values. Percentages will be rounded to one decimal place, unless otherwise specified.

In general, all eyes of all subjects will be included in analyses, unless otherwise noted. The primary efficacy analysis will be conducted at a significance level of 0.05. Hypothesis testing for the key secondary objectives will be conducted with significance determined at the 0.05 level with multiple testing adjustments (Refer to [Section 6.2.1](#)). For most analyses, when a hypothesis test is performed, it will be comparing the ALK-001 and Placebo treatment arms. Confidence intervals will generally be given at a level to mimic the significance level (95% CIs for 0.05 significance level) unless otherwise noted.

Unless otherwise specified, the following treatment arms will generally be included in tables, listings, and figures:

- ALK-001: Subjects randomized to 24 months of ALK-001 at 14 mg per day
- Placebo: Subjects randomized to 24 months of placebo

All analyses will be conducted in SAS®, Version 9.4 or higher (SAS Institute Inc., Cary, NC) or in R, Version 3.6.0 or higher (R Core Team 2019).

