4.7. Derived Variables and Parameters

Variables requiring calculation will be derived using the following formulas:

- Duration of study (month) = (last study participation date – informed consent date +1)/ 30.4375
- Duration of exposure (day) = last treatment date – reference start date +1
- Duration of exposure (month) = duration of exposure (day)/30.4375
- Percentage of duration of exposure (%) is calculated as [total number of days with no lapse in treatment (day)]/ [duration of exposure (day)] x 100.
- Change from baseline = postbaseline value – baseline value
- Percentage change from baseline = ([postbaseline value – baseline value] / baseline value) x 100
- Low Luminance Deficit (LLD) = one eye's Best Corrected Visual Acuity (BCVA) score – Low Luminance Visual Acuity (LLVA) score

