6.1. Analyses of Primary Efficacy Endpoint

An Eligible Eye is defined as an eye with (a) measurable GA and (b) no presence of CNV at baseline as determined centrally by a central reading center according to combined review of optical coherence tomography (OCT) and color fundus photograph (CFP) (“Multimodal imaging”), and FA. GA lesion size will be measured independently by three readers on FAF imaging. The final GA lesion size (area) for each subject’s Eligible Eye, adjudicated from the assessments by three readers, will be used in the analysis.

The primary efficacy endpoint is the mean rate of growth (slope) in the GA area as measured by FAF from baseline to Month 24.

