6.1.3 Main Analysis of Primary Efficacy Endpoint

The mean rates of change (slope) in the GA area will be computed for the ALK-001 and the placebo arms, by use of a linear mixed-effects model applied to the GA area measured on FAF images at time points (baseline, Month 6, Month 12, Month 18 and Month 24) assuming time as continuous and linear (“slope model”).

The analysis model will use the change from baseline in the GA area measured by FAF as the response variable, and will include treatment arm (ALK-001, placebo), pattern of FAF at the junctional zone of GA (banded/diffuse, focal/other/cannot grade), GA lesion multifocality (multifocal, unifocal/other/cannot grade) and foveal status (foveal sparing, subfoveal/cannot grade) as fixed effects, baseline GA lesion area and time (year, continuous assuming linearity) as

covariates, time \times treatment interaction, and baseline GA lesion area \times time interaction. Random effects include subject and subject's eye (OD or OS). A common unstructured covariance matrix will be used to model the within-subject errors, and the Kenward-Roger's (Kenward and Roger 1997) method will be used to estimate denominator degrees of freedom. If the model fails to converge, alternative structures (heterogenous autoregressive (1), heterogeneous compound symmetry, autoregressive (1), or compound symmetry, in this order) will be considered.

The mean rate of change (mm^2/year), standard error, and 95% confidence interval (CI) will be estimated from baseline to Month 24 for each treatment arm. The estimated difference in slopes among the treatment groups along with the 95% CIs and p-value will be provided to test the significance of the treatment effect.

The observed values for the GA area (mm^2) of Eligible Eyes will be summarized by treatment group and visit. Summaries will present the descriptive statistics for baseline, absolute values and change from baseline data.

The mean change from baseline \pm the standard error in the GA area (mm^2) of Eligible Eyes as well as the Least-Squares (LS) mean of the change from baseline \pm the standard error in GA area (mm^2) of Eligible Eyes will be plotted over time by treatment group.

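### The percentage-change sensitivity analysis sets no minimum baseline lesion area, so if very small fellow-eye lesions are present, a few of them could dominate its variance

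*SAP*

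**What the plan says.** The Month 24 percentage-change bullet in SAP 6.1.5.3 repeats the main model "using percentage change from baseline in GA lesion area as response variable, assuming time as categorical", and it does so twice: once on area, once on its square root. SAP 4.7 fixes the formula: "Percentage change from baseline = ([postbaseline value – baseline value] / baseline value) x 100". Baseline is the denominator.

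The eyes are those of the main analysis. SAP 6.1 states: "An Eligible Eye is defined as an eye with (a) measurable GA and (b) no presence of CNV at baseline". No minimum area is given. SAP 4.1 adds: "In general, all eyes of all subjects will be included in analyses, unless otherwise noted". SAP 6.1.3 fits random effects for both subject and eye, so two eyes of one subject can enter.

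Protocol v1.1, section 1.8.1, limits the study eye to about 1.5–20 mm² (criterion 9). Criterion 16 lets the fellow eye have GA of any size.

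SAP 6.1.5.3 contains one floor, in a separate bullet: "subject eyes are included only if GA lesion at baseline exceeds 0.5" mm². Each bullet modifies the main analysis, and nothing attaches this one to the percentage-change bullet.

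**The concern.** Dividing by baseline area turns similar absolute growth into very different percentages. An eye with a tiny lesion can show a change of many hundred percent while most eyes show tens of percent. A normal-theory mixed model gives such values great leverage on the residual variance and on the arm difference. The model's linear baseline-area term does not remove a dependence on 1/baseline.

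A sensitivity analysis is there to test whether the primary result is robust. If a handful of eyes carries most of the variance, a null result says little but could be read as contradicting the primary analysis. The 0.5 mm² bullet shows that the sponsor foresaw small lesions. It tests them on the absolute scale, where they matter least, and not on the percentage scale, where they matter most.

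**Working it through.** The SAP gives no figure for this analysis, so there is none to reproduce.

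**Inputs from the documents.** Growth 1.8 mm²/year with SD 1.2, 200 subjects with 80% evaluable, 33% slowing (SAP 3.2); 2:1 allocation (SAP 3.1); the SAP 4.7 formula.

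**Assumed, because the documents are silent.** The number and sizes of fellow-eye lesions, the smallest measurable lesion, and how growth depends on size.

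**Step 1: one eye.** Constant area growth over 24 months is 1.8 × 2 = 3.6 mm², so the percentage is 3.6 / baseline × 100. Under an assumed square-root growth of 0.3 mm/year it is [(√baseline + 0.6)² / baseline − 1] × 100.

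| Baseline (mm²) | Constant area growth | Square-root growth |
|---|---|---|
| 20 | 18% | 29% |
| 7.5 | 48% | 49% |
| 1.5 | 240% | 122% |
| 0.5 | 720% | 242% |
| 0.25 | 1,440% | 384% |
| 0.1 | 3,600% | 739% |

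**Step 2: share of the total sum of squares.** Simulated eyes: 60% uniform on 1.5–20 mm²; the other 40% either uniform on 0.1–20 mm² or lognormal (median 3, log-SD 1.2). Constant-growth runs used gamma 24-month growth with mean 3.6 and SD 2.4 mm². Square-root runs used an assumed 0.32 (SD 0.15) mm/year. Eyes under 0.5 mm² make up 0.8% of the uniform mix (0.4 × 0.4/19.9) and about 2.7% of the lognormal mix. Their share is:

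- constant area growth: 78–84%;
- square-root growth: 53–63%;
- square-root growth, with nothing under 0.25 mm² counted as measurable: 25–36%.

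**Step 3: a trial-sized data set.** 160 evaluable subjects (200 × 0.80) split 107/53, plus 80 assumed fellow eyes with GA, give 240 eyes. Month 24 percentage change was regressed on arm and baseline area with a true 33% effect, 1,500 runs per scenario. This is simpler than the SAP model: one visit, no subject effect. Tiny eyes lie at 0.05–0.5 mm² unless stated; all others at 1.5–20 mm². SE is for the arm difference in percentage points; P is the chance of significance favouring ALK-001.

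| Tiny eyes of 240 | Constant: SE | P | Tiny-eye share | Square-root: SE | P | Tiny-eye share |
|---|---|---|---|---|---|---|
| 0 | 5.3 | 0.88 | 0 | 3.3 | 1.00 | 0 |
| 2 | about 31 | 0.20 | about 85% | about 7 | 0.81–0.83 | 59–60% |
| 5 | 53–55 | 0.10–0.12 | 96% | 11.8 | about 0.60 | 83% |
| 5, at 0.25–0.5 mm² | 18 | 0.27 | 84% | 5.8 | 0.96 | 59% |
| 10 | 78 | 0.10 | – | 16.6 | 0.48 | 91% |
| 10, floor applied | 5.4 | 0.88 | 0 | 3.3 | 1.00 | 0 |

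With five tiny eyes at 0.05–0.5 mm², the conclusion differed from that of the floored analysis in 78% of runs (constant) or 40% (square-root). The estimate had the wrong sign in 35% or 2%.

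**Step 4: the square-root-area version.** With five tiny eyes, P was 0.27 (constant) or 0.89 (square-root growth), against 0.10 and 0.60 for percentage change in area in the same set of runs. In the absolute-change analysis tiny eyes held 3% or less of the sum of squares.

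**Step 5: the floor under the Step 2 mixes.** Step 3 has no eyes between 0.5 and 1.5 mm², which flatters the floor. The Step 2 mixes include them. There, P rose from 0.30–0.38 to 0.54–0.67 (constant) and from 0.90–0.96 to 0.99–1.00 (square-root).

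**Step 6: no treatment effect.** Rejection at the nominal 5% level was 3–5% under both mixes and both growth laws.

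**The case against.** The best counter-argument is that the size rests on assumptions. No section gives the number or sizes of small fellow-eye lesions, or the smallest lesion the reading center would call measurable. Constant area growth is the harshest law: SAP 3.2 states 1.8 mm²/year as an average, and the SAP allows growth to depend on size through the baseline area × time term and the square-root analyses. The lognormal mix has no lower bound and produces lesions down to about 0.01 mm². All of this stands, and it is why the effect is given as a range.

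The same bullet also plans the less affected square-root version. The analysis lies outside the primary test (SAP 6.1.2) and the fixed sequence (SAP 6.2.1). The other area-based analyses in SAP 6.1.5.3 do not divide by baseline. These points stand too, and they limit the consequence.

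Two stronger readings are tempting. A reader might infer that tiny lesions determine the result; without their number and sizes, the documents support only that they could dominate it. A reader might also infer that the analysis could falsely support the primary result through excess false positives; the null runs show no inflation. Chance imbalance between arms can still move the point estimate, but a wide interval would show it.

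**Conclusion.** The gap is in the text: the percentage-change analyses have no lower limit on baseline area, and the SAP's only floor is not applied to them. The consequence is conditional. If a few fellow eyes have lesions under about 0.5 mm², the analysis of percentage change in area loses precision and its estimate becomes unstable. The loss runs from slight (P 0.96 against 1.00 with five eyes at 0.25–0.5 mm² and square-root growth) to severe (0.10–0.12 against 0.88 with five eyes at 0.05–0.5 mm² and constant growth). If there are no such eyes, nothing changes. This rests on the assumed lesion mixes, on two growth laws, and on a single-visit model without a subject effect. It is a cheap improvement to a supportive analysis, not a threat to the trial's main conclusions.

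**What to change.** Add one clause to the percentage-change bullet in SAP 6.1.5.3: both percentage-change analyses, on area and on square-root area, include only eyes with baseline GA area above 0.5 mm². If wanted, show the unrestricted versions beside them as supportive. This reuses a threshold the SAP already contains, so no new cut-off needs defending. It should be fixed before unmasking; a floor added afterwards should be labelled post hoc.

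The cost is the exclusion of a few eyes. The floor does not make percentages homogeneous: at constant growth a 0.5 mm² lesion still shows 720% against 18% at 20 mm².

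An optional alternative is to analyse ln(area at visit / baseline area) and back-transform. In simulation this cut the small eyes' share of the sum of squares to about 25–34% without excluding any, but it changes the quantity estimated to a ratio of geometric means.

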6.1.6 Subgroup Analyses of Primary Efficacy Endpoint

Subgroup analyses will be performed to evaluate the consistency of the primary analysis results across subgroups defined by demographic and baseline characteristics. The main analysis described in [Section 6.1.3](#) will be repeated for the primary efficacy endpoint for each of the following subgroups:

- **Age group:** <75 years, ≥75 years at enrollment
- **Sex:** male, female
- **Baseline BCVA:** BCVA 64 letters (~20/50) or better, BCVA less than 64 letters
- **Baseline LLD:** LLD 30 letters or more, LLD less than 30 letters
- **Baseline GA lesion size:** small (< 7.5 mm²), large (≥ 7.5 mm²)
- **Baseline GA lesion multifocality:** multifocal, unifocal
- **Baseline GA lesion foveal status:** foveal sparing, subfoveal

Forest plot will be produced for mean rate of change (mm²/year) or slope of total GA area (mm²) from the baseline to Month 24 for each treatment arm, difference in mean rate of change and associated 95% CI for overall population and by subgroups.

6.2. Analyses of Key Secondary Efficacy Endpoints

The key secondary efficacy endpoints are listed in [Section 2.2.2](#). Formal hypothesis testing for key secondary endpoints, evaluated based on data from baseline to Month 24 for LLVA and BCVA, will be performed.

Hypothesis testing for two key secondary efficacy endpoints will be performed in the manner specified in [Section 6.2.1](#).

6.2.1 Hypotheses Testing and Type I Error Management

If the hypothesis test for the primary endpoint is statistically significant favoring ALK-001, then hypotheses testing will be performed for the key secondary endpoints. The null (H_{2a}, H_{3a}) and alternative (H_{2b}, H_{3b}) hypotheses for the key secondary efficacy endpoints are the following:

- H_{2a}: There is no difference between ALK-001 and Placebo regarding mean change from baseline in LLVA score at Month 24, as assessed by an ETDRS chart or an EVA system.
- H_{2b}: There is difference between ALK-001 and Placebo regarding mean change from baseline in LLVA score at Month 24, as assessed by an ETDRS chart or an EVA system.
- H_{3a}: There is no difference between ALK-001 and Placebo regarding mean change from baseline in BCVA score at Month 24, as assessed by an ETDRS chart or an EVA system.
- H_{3b}: There is difference between ALK-001 and Placebo regarding mean change from baseline in BCVA score at Month 24, as assessed by an ETDRS chart or an EVA system.

To control type I error, hypotheses for the key secondary efficacy endpoints will be tested in a fixed sequencing order, first for H_{2a}, followed by H_{3a}, based on a two-sided alpha level of 0.05. Sequential testing will continue as long as all preceding hypotheses can successfully be rejected at alpha level of 0.05 favoring ALK-001.

6.2.2 Low Luminance Visual Acuity (LLVA)

LLVA is measured using a letter score in an equivalent manner by either an ETDRS chart or an EVA system for each eye at visits V01 (Screening), V04 (Month 6), V06 (Month 12), V08 (Month 18), and V10 (Month 24).

The LLVA score at time points (baseline, Month 6, Month 12, Month 18 and Month 24) from Eligible Eyes will be summarized and analyzed using mixed effect model for repeated measure (MMRM). The analysis model will use change from baseline in LLVA score as the response variable, and will include treatment arm (ALK-001, placebo), pattern of FAF at the junctional zone of GA (banded/diffuse, focal/other/cannot grade), GA lesion multifocality (multifocal, unifocal/other/cannot grade), foveal status (foveal sparing, subfoveal/cannot grade) and time (year, categorical) as fixed effects, baseline GA lesion area and baseline LLVA score as covariates, time (year, categorical) \times treatment and baseline LLVA score \times time (year, categorical) interaction terms, subject and subject's eye (OD or OS) as random effects. A common unstructured covariance matrix will be used to model the within-subject errors, and the Kenward-Roger's (Kenward and Roger 1997) method will be used to estimate denominator degrees of freedom. If the model fails to converge, alternative structures (heterogenous autoregressive (1), heterogeneous compound symmetry, autoregressive (1), or compound symmetry, in this order) will be considered.

The LS mean of the change from baseline in LLVA score of Eligible Eyes, standard error, and 95% confidence interval (CI) will be estimated from baseline to Month 24 for each treatment arm. The estimated difference in change from baseline among the treatment groups along with the 95% CIs and p-value will be provided to test the significance of the treatment effect.

The observed values for LLVA score of Eligible Eyes will be summarized by treatment group and visit. Summaries will present the descriptive statistics for baseline, absolute values and change from baseline data.

The mean change from baseline in LLVA score of Eligible Eyes \pm the standard error as well as the LS mean of the change from baseline in LLVA score of Eligible Eyes \pm the standard error will be plotted over time by treatment group.

The categorical changes (a decrease of greater than 15, a decrease greater than 7 to 15, little change from baseline [≤ 7], an increase of greater than 7 to 15, and an increase of greater than 15) for Eligible Eyes will be summarized by treatment group and visit.

6.2.3 Best Corrected Visual Acuity (BCVA)

BCVA is measured using a letter score in an equivalent manner by either an ETDRS chart or an EVA system for each eye at visits V01 (Screening), V04 (Month 6), V06 (Month 12), V08 (Month 18), and V10 (Month 24).

An analysis that mirrors that of LLVA in [Section 6.2.2](#) will be repeated for BCVA.

6.3. Analyses of Secondary Efficacy Endpoints

All secondary efficacy analyses will be performed using the Full Analysis Set (FAS) unless otherwise noted.

6.3.1 Low Luminance Deficit (LLD)

The low luminance deficit (LLD) score is computed as the difference between one eye's BCVA and LLVA scores.

The LLD score at time points (baseline, Month 6, Month 12, Month 18 and Month 24) from Eligible Eyes will be summarized and analyzed in a similar way using MMRM described in [Section 6.2.2](#). The analysis model will use change from baseline in LLD score as the response variable, and will include treatment arm (ALK-001, placebo), pattern of FAF at the junctional zone of GA (banded/diffuse, focal/other/cannot grade), GA lesion multifocality (multifocal, unifocal/other/cannot grade), foveal status (foveal sparing, subfoveal/cannot grade) and time (year, categorical) as fixed effects, baseline GA lesion area and baseline LLD score as covariates, time (year, categorical) \times treatment and baseline LLD score \times time (year, categorical) interaction terms, subject and subject's eye (OD or OS) as random effects. A common unstructured covariance matrix will be used to model the within-subject errors, and the Kenward-Roger's (Kenward and Roger 1997) method will be used to estimate denominator degrees of freedom. If the model fails to converge, alternative structures (heterogenous autoregressive (1), heterogeneous compound symmetry, autoregressive (1), or compound symmetry, in this order) will be considered.

The LS mean of the change from baseline in LLD score of Eligible Eyes, standard error, and 95% confidence interval (CI) will be estimated from baseline to Month 24 for each treatment arm. The estimated difference in change from baseline among the treatment groups along with the 95% CIs and p-value will be provided to test the significance of the treatment effect.

The observed values for LLD score of Eligible Eyes will be summarized by treatment group and visit. Summaries will present the descriptive statistics for baseline, absolute values and change from baseline data.

The mean change from baseline in LLD score of Eligible Eyes \pm the standard error as well as the LS mean of the change from baseline in LLD score of Eligible Eyes \pm the standard error will be plotted over time by treatment group.

